# 6.1.1.4 Recording Adverse Events

The AE recording into the eCRF will extend from the signing of the ICF until completion of final visit. All AEs will be followed until they are resolved or stabilized; however, if AEs are ongoing at the time of the last study visit, only treatment-related AEs will be followed beyond 26 weeks after investigational drug administration.

All AEs, regardless of the relationship to study drug, will be recorded in the eCRF system.

All AE reports should contain a brief description of the event, date and time of onset, date and time of resolution, intensity, treatment required, relationship to study drug, action taken with the study drug, outcome, and whether the event is classified as serious.

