#### 3.2.2 Secondary Efficacy Endpoints

The following secondary efficacy endpoints will be assessed at the times specified in the schedule of events and overall time-course, and changes from baseline will be analyzed:

- Worst leg pain during the past 24 hours assessed by VAS.
- Worst back pain during the past 24 hours assessed by VAS.
- Functional disability measured by the Oswestry Disability Index (ODI).
- Change of neurological status from baseline determined by neurological examinations:
  - Femoral Nerve Stretching (FNS) test for patients with lumbar disc herniation L1–L2, L2–L3, or L3–L4 or
  - Straight Leg Raising (SLR) test [for patients with lumbar disc herniation L4–L5 or L5–S1, and
  - Sensation, muscle strength, and deep tendon reflex.
- Occurrence of post-treatment surgery for lumbar disc herniation at the same level of administration of the investigational drug up to Week 26 including patients who discontinued from the study.

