#### 4.3.1 Patient Withdrawal Criteria

The Investigator will withdraw a patient from the clinical study if any of the following situations occur:

- 1. When the patient withdraws his or her consent
- 2. When the occurrence of an AE, such as noted below, leads the Investigator to judge it necessary for the patient to have surgical intervention or to withdraw the patient from the clinical study:
  - Significant neurologic deficit, e.g., progressive weakness or sudden loss of muscle strength in L1–L2, L2–L3, L3–L4, L4–L5 or L5–S1 innervated muscles, bowel or bladder dysfunction, or other signs and symptoms of cauda equine/conus medullaris involvement, or
  - Abnormal X-ray or MRI findings coupled with correlating clinical symptoms posing safety concerns
- 3. When a poor response to the investigational drug leads the Investigator to judge it necessary to perform a surgical intervention for back pain/leg pain or to withdraw the patient from the clinical study

- 4. If the Investigator judges it inappropriate to include a patient in the efficacy/safety assessment
- 5. If a patient becomes pregnant
- 6. Others:
  - No investigational drug could be administered.
  - The continuation of the study makes the risk to a patient's health unacceptable.
  - The Sponsor prematurely terminates the study.
  - The Investigator judges it necessary to withdraw a patient from the study.

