#### 5.8.2 Prohibited Concomitant Therapies

Lumbar operation, lumbar percutaneous nucleotomy, or lumbar intradiscal therapies (e.g., chemonucleolysis, intradiscal electrothermal treatment) for treatment of back pain and leg pain are prohibited from the time of informed consent up to the final observation (Week 26 after investigational drug administration). A patient who requires lumbar operation, lumbar percutaneous nucleotomy, or lumbar intradiscal therapies (e.g., chemonucleolysis or intradiscal electrothermal treatment) in the clinical study period must be discontinued from the clinical study.

In addition, discography for diagnostic purpose is also prohibited from the time of informed consent through Week 13 after investigational drug administration.

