#### 7 STUDY CONDUCT

#### 7.1 Schedule of Procedures

Each patient will be asked to complete 6 study visits including a screening evaluation:

- Screening visit
- Treatment Day 0
- Evaluation period/Follow-up visits at Week 1, Week 6, Week 13, and Week 26
- Patients terminating the study early will be asked to complete a discontinuation visit.

Table 3:         Schedule of Assessments and Procedures								
Observation Period	Before 4 Weeks (Day -28 to Day 0)	Treatment	Day 0	Week 1	Week 6	Week 13	Week 26	Upon Discontinuation
	Outpatient a							Upon Disc
Observation / Examination Items	Screening Period	Evaluation Period/ Evaluation Period/ Follow-up						
	Visit 1	Visi	it 2	Visit 3	Visit 4	Visit 5	Visit 6	
Permissible lag time for				±3D	±14D	±14D	±14D	+14D
observation/examination Verify conformance with entry criteria Obtain informed consent	Х							
Patient characteristics	Х							
Serum/urine pregnancy test b	Х	Х						
Patient enrollment		Х						
Administration of the investigational drug		▼						
Pain assessment by patients (VAS)	Х	Х		Х	Х	Х	Х	Х
ODI		Х		Х	Х	Х	Х	Х
Physical examination	Х	Х						
Neurological examination	Х			Х	Х	Х	Х	Х
Imaging (X-ray, MRI) c	Х				Х	Х	Х	Х
Vital signs	Х	Х	Х	Х	Х	Х		Х
Laboratory tests	X			Х	Х	Х		X
Serum anti-SI-6603 antibody d		Х				Х	Х	Х
Concomitant drug/therapy								→ X
AE/SAE								> x
Record occurrence of lumbar surgery e								⇒ X

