#### **Procedures by Visit** 7.2

Visits should occur within the time indicated for each scheduled visit. All times should

<sup>*a* Hospitalization on the day at administration is allowed if it is required by the site.

<sup>b Serum pregnancy test will be performed at Screening, and urine pregnancy test will be performed at *Visit 2 before administration of the investigational drug.* 

<sup>c If repeat imaging is needed, the permissible lag time will be extended by a maximum of an additional 14 days.

<sup>d Examined when considered necessary in unscheduled visit

<sup>e Patients who discontinued the study will be followed until the Week 26 visit.

be recorded using the 24-hour clock (e.g., 23:20, not 11:20 pm).

- 7.2.1 Screening (Visit 1)
  - Obtain written informed consent
  - Record demographic and medical history
  - Record the use of concomitant drug/therapy
  - Document occurrence of lumbar surgery
  - Verify conformance with entry criteria
  - Perform vital signs assessments (temperature, blood pressure, heart and respiration rate)
  - Perform physical examination
  - Perform neurological examination
  - Complete pain assessment (VAS)
  - Perform imaging tests (X-ray and MRI)
  - Obtain study entry laboratory specimens (blood for HIV; pregnancy [for women of childbearing potential]; and hematology, hepatic, and chemistry panels)

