#### 7.2.7 Discontinuation Visit

- Complete pain assessment (VAS) and ODI
- Record concomitant drug and therapy information, including drugs or therapy used to treat an AE
- Record AEs and SAEs since previous visit
- Document occurrence of lumbar surgery
- Perform vital sign assessments (temperature, blood pressure, heart and respiration rate)
- Perform neurological examination
- Perform imaging tests (X-ray and MRI)
- Obtain laboratory specimens (blood for hematology, hepatic, and chemistry panels)
- Obtain blood specimen for serum anti-SI-6603 antibody

Patients who discontinue early from the study should, if possible, have a Discontinuation Visit. This visit should take place as soon as possible after it was learned that the patient will not be able to complete the study (see also Section 4.3).

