# 9.9 Duration of the Study

For an individual patient, the maximum duration of the study will be up to 30 weeks (including up to 4 weeks for screening, 1 day treatment and up to 26 weeks follow-up). The study will close when the last patient has completed the Visit Week 26 or the Discontinuation Visit.

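### No contact is scheduled to find new non-serious AEs between withdrawal and Week 26, yet withdrawn patients stay in the AE denominator; the bias is downward, probably modest, and cheap to prevent

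*Combined protocol and SAP*

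**What the plan says.** Section 6.1.1.4 sets the AE window: "The AE recording into the eCRF will extend from the signing of the ICF until completion of final visit". The final visit is not defined.

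Withdrawal is partly tied to outcome. Under section 5.8.2, a patient who needs lumbar operation, percutaneous nucleotomy or intradiscal therapy "in the clinical study period must be discontinued from the clinical study". Section 4.3.1 adds AEs that lead the Investigator to judge surgery or withdrawal necessary, and also: "When a poor response to the investigational drug leads the Investigator to judge it necessary to perform a surgical intervention for back pain/leg pain".

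On what happens next, section 7.2.7 says: "Patients who discontinue early from the study should, if possible, have a Discontinuation Visit". At that visit AEs are recorded back to the previous visit. Section 9.9 allows closure on the same visit: "The study will close when the last patient has completed the Visit Week 26 or the Discontinuation Visit".

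Three things continue after withdrawal:
- **Lumbar surgery.** The Table 3 row "Record occurrence of lumbar surgery" carries footnote e: "Patients who discontinued the study will be followed until the Week 26 visit". The surgery endpoint in section 3.2.2 runs "up to Week 26 including patients who discontinued from the study".
- **SAEs**, up to 26 weeks after the dose (section 6.1.1.5).
- **AEs already open**, until resolved, stabilized or explained (sections 6.1.1.4 and 6.1.1.6).

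The AE/SAE row of Table 3 carries no such footnote. The safety population is all treated patients (section 8.1.2), AE incidence is given with a 95% CI and no stated exposure adjustment (section 8.6.1), and safety data are in general not imputed (section 8.2).

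**The concern.** Treatment is one injection on Day 0. Leaving the study takes away no exposure; it only ends observation. A withdrawn patient is still at risk up to Week 26 and still counts in the denominator, so a new non-serious AE that nobody asks about is analysed as no event.

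The primary objective is safety over 26 weeks (section 2.1), and this drug's known profile is mostly non-serious. In earlier studies, pooled over doses, 2 of 269 treated patients had a related SAE (section 1.3.1.1), against 64 of 269 with related back pain alone (section 1.3.1.3). Following only SAEs after withdrawal would see little of that profile. There is no comparator arm against which a shortfall might show. Section 8 leaves analysis detail to an SAP, which can adjust for exposure but cannot restore events that were never collected.

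**Working it through.** **Step 1: the passages side by side, for a patient who withdraws.**

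| Item | Pursued to Week 26 after withdrawal? | Where |
|---|---|---|
| Lumbar surgery | Yes | 3.2.2; Table 3 footnote e |
| SAEs | Yes, 26 weeks after dose | 6.1.1.5 |
| AEs already open | Yes, until resolved, stabilized or explained | 6.1.1.4, 6.1.1.6 |
| New non-serious AEs | No contact scheduled | 6.1.1.4, 7.2.7, Table 3 AE/SAE row |

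**Step 2: direction.** The denominator is fixed at all treated patients, and an uncollected first event can only lower the numerator. All-cause incidence is therefore biased downward or not at all.

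**Step 3: the plan's own precision figures.** Section 8.8 gives Clopper-Pearson 95% CIs. Recomputed:
- 3/1000: 0.062% to 0.874% (stated 0.06%, 0.87%)
- 15/1000: 0.842% to 2.462% (stated 0.84%, 2.46%)

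Both agree. They cover sampling error only and treat all 1000 patients as observed to Week 26.

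**Step 4: size.** Inputs:
- N = 1000 (section 8.8).
- w, the share withdrawn: not in the documents; assumed 5–10%, with 2% as a low case.
- q, the share of withdrawn patients whose first event of a given term falls after withdrawal: not in the documents; assumed 10–24% for a common term. The top is the earlier rate of related back pain, 64/269 = 23.8%.

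Shortfall in incidence = w × q.
- w = 0.05, q = 0.10: 0.5 points (5 patients)
- w = 0.10, q = 0.238: 2.4 points (about 24 patients)
- w = 0.02, q = 0.238: 0.48 points

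CI half-width at 23.8% = 1.96 × √(0.238 × 0.762 / 1000) = 2.64 points. At w = 10%, q would have to exceed 2.64 / 10 = 26.4% for the shortfall to pass the half-width. That is above the rate seen over the whole follow-up of the earlier studies.

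For the 1.5% event of section 8.8, at the same risk in withdrawn patients, the number missed = 1000 × w × 0.015:
- w = 0.05: 0.75 patients
- w = 0.10: 1.5 patients

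Reading 14 instead of 15 moves the interval from 0.84–2.46% to 0.77–2.34%.

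**The case against.** **The meaning of the final visit is inferred.** Section 5.8.2 equates the final observation with Week 26, section 6.1.1.4 pairs the last study visit with 26 weeks, and footnote e is worded generally. One could read these as extending AE recording to Week 26 for everyone. This stands as far as it goes: the protocol does not state that AE collection stops at withdrawal, and a reader who infers an explicit rule to that effect goes too far. But none of these passages schedules an enquiry about new non-serious AEs, and the footnote is attached to another row.

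**What remains is narrow.** SAEs, surgery and open AEs are covered, the AE that led to withdrawal is already counted, and pain the Investigator judges clinically aggravated is itself reportable as an AE (section 6.1.7). This stands, and it limits the point to new non-serious events.

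**Earlier AE discontinuations do not point to the drug.** In the USA Phase II study 2 of 18 (11.1%) left for an AE, none of them treatment-related (section 1.1.2.6). In the Japanese Phase III study the five reported were all on placebo, with no causal relationship established (section 1.1.2.7). This stands: these figures do not show that treatment-related AEs drive patients out of follow-up.

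**AEs after surgery are confounded with the operation.** Section 1.3.1.4 itself cites disc height loss and Modic changes after discectomy. This stands as a reason to flag such events and report incidence both ways, but not as a reason to leave them uncollected.

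**Two stronger readings are tempting.** One is that the bias swamps the confidence intervals. That needs withdrawn patients to have clearly raised risk, falling mostly after they leave, and no document figure supports it. The other is that the by-visit pain, disability and imaging summaries are flawed for the same reason. Sections 8 and 8.2 leave missing-data handling for efficacy to the SAP, so the protocol does not establish that flaw.

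**Conclusion.** The gap is real, though it rests on reading an undefined term together with sections 7.2.7 and 9.9 and the placement of footnote e. All-cause incidence of non-serious AEs over 26 weeks can only be understated. Not every withdrawal is outcome-related, but some grounds are, so those who leave cannot be assumed to resemble those who stay.

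The size is unknown because the documents give no withdrawal rate. Under the assumptions shown it is about 0.5–2.4 points for a common term, inside the 2.6-point half-width, under 0.5 points if 2% withdraw, and about 0.75–1.5 patients for a 1.5% event. The bias is probably modest. The case for acting is that the loss touches the primary objective, cannot be repaired at analysis and costs little to prevent. This is a cheap improvement, not a fault that invalidates the study.

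**What to change.** - In section 6.1.1.4 and Table 3, state that for patients who discontinue without withdrawing consent to follow-up, recording of all AEs, serious and non-serious, runs to Week 26. Do this by extending footnote e to the AE/SAE row and using the follow-up already required for lumbar surgery.
- Flag AEs that start after lumbar surgery or intradiscal therapy, and report incidence with and without them.
- Align section 9.9 so that the study does not close before this follow-up is complete.

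The withdrawal rules are unchanged and no imaging is added. Asymptomatic imaging AEs after withdrawal would remain unseen, as would any AE in patients who refuse all follow-up; state both as limitations.

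**Cost.** Up to one contact per withdrawn patient (50–100 contacts if 5–10% of 1000 withdraw), fewer if surgery is already to be traced by contact, which footnote e does not say. Each event reported also needs the full AE record that section 6.1.1.4 requires. Expect some recall error and some post-surgery AEs that are hard to attribute.

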#### 6.1.1.5 Reporting Serious Adverse Events

All SAEs that occur during the period of observation, and all SAEs occurring up to 26 weeks after receiving the dose of study drug, whether considered to be associated with the study drug or not, must be reported within 24 hours by fax, email or telephone to the PAREXEL Safety Contact using the numbers, and specific mailbox in the List of Study Personnel.

Any SAE occurring after the end of the study should be reported to the Sponsor/PAREXEL by the Investigator if the Investigator considers there is a causal relationship with the study drug.

[figure not shown]
The minimum information required for an initial report is:

- Name of person sending the report (i.e., name, address of Investigator)
- Patient identification (screening/randomization number, initials, NOT patient name)
- Protocol number
- Description of SAE
- Causality assessment, if possible.

However, as far as possible all points on the SAE form should be covered in the initial report, or the completed SAE form itself must be faxed to the PAREXEL Safety Contact. In addition, the event must be documented in the eCRF.

In case the PAREXEL Safety Contact cannot be contacted (e.g., out of normal working hours or at weekends), SAE reports will be received by PAREXEL. The required information should be faxed, emailed or a message should be left on the voicemail service (for phone/fax/email, see the contacts in the List of Study Personnel).

After receipt of the initial report, the safety center will review the information and, if necessary, contact the Investigator, to obtain further information for assessment of the event. PAREXEL will be responsible for all information processing and reporting according to local legal requirements. Where necessary, Investigators will inform Regulatory Authorities in their own countries.

Details for the reporting of Suspected Unexpected Serious Adverse Reactions (SUSARs) can be found in Section 6.1.1.7.

# 6.1.1.6 Follow-up of Adverse Events

During the study, all AEs experienced by a patient, irrespective of the suspected causality, will be monitored until the AE has resolved, any abnormal laboratory values have returned to baseline or stabilized at a level acceptable to the Investigator and Medical Monitor, until there is a satisfactory explanation for the changes observed, until the patient is lost to follow-up, or until the patient has died. If the AEs are ongoing at the time of the last study visit, only treatment-related AEs will be followed beyond 26 weeks after investigational drug administration until the AE has resolved, any abnormal laboratory values have returned to baseline or stabilized at a level acceptable to the Investigator and Medical Monitor, or until there is a satisfactory explanation for the changes observed. Follow-up of the AEs beyond the entire study duration will be evaluated on case-by-case basis by the Medical Monitor and the Sponsor.

# 6.1.1.7 Suspected Unexpected Serious Adverse Reactions

Any AE that is serious, associated with the use of the study drug, and unexpected (SUSAR) has additional reporting requirements, will be reported to regulatory authorities and Independent Ethic Committees (IECs) according to the local requirements.

The Sponsor will notify the Investigators in a timely fashion of relevant information about SUSARs that could adversely affect the safety of patients. Follow-up information may be submitted if necessary.

The Sponsor will also provide annual safety updates to the Regulatory Authorities and IECs responsible for the study. These updates will include information on SUSARs and other relevant safety findings.

# 6.1.1.8 Pregnancy

The Sponsor has a responsibility to monitor the outcome of pregnancies where there has been maternal exposure to the study drug.

Pregnancy alone is not regarded as an AE unless there is a suspicion that the study drug may have interfered with the effectiveness of a contraceptive medication.

Elective abortions without complications should not be handled as AEs, unless they were therapeutic abortions (see below). Hospitalization for normal delivery of a healthy newborn should not be considered a SAE.

All pregnancies must be reported by the Investigator to PAREXEL on the initial pregnancy report form within 30 days after becoming aware of the pregnancy. The Investigator must follow up and document the course and the outcome of all pregnancies even if the patient was discontinued from the study or if the study has finished.

All outcomes of pregnancy must be reported by the Investigator to PAREXEL/Sponsor on the pregnancy outcome report form within 30 days after he or she has gained knowledge of the normal delivery or elective abortion.

Any SAE that occurs during pregnancy (including SAEs occurring after last administration of study drug) must be recorded on the SAE report form (e.g., maternal serious complications, spontaneous or therapeutic abortion, ectopic pregnancy, stillbirth, neonatal death, congenital anomaly, or birth defect) and reported within 24 hours in accordance with the procedure for reporting SAEs.

If a female partner of a male study patient who has been exposed to the investigational drug becomes pregnant before the end of Week 26, the pregnancy and outcome of pregnancy should be reported.

# 6.1.2 Laboratory Variables

Laboratory assessments will be performed by a central laboratory, as identified in the List of Study Personnel. The Investigator or site staff will collect blood samples according to the "Investigator Laboratory Manual for SI-6603" separately specified.

The following laboratory variables will be determined in accordance with schedule of assessments Table 3.

Table 2:	Laboratory As	ssessments	
Hematology:	hemoglobin hematocrit platelets red blood cell count white blood cell count with differential		
Clinical chemistry:	creatinine C-reactive protein	Liver enzymes:	alkaline phosphatase Aspartate aminotransferase (AST) Alanine aminotransferase (ALT)

	total protein direct bilirubin total bilirubin total cholesterol triglycerides urea nitrogen uric acid		lactic dehydrogenase γ-glutamyl transpeptidase albumin	
Electrolytes:	calcium chloride magnesium potassium sodium	Serological marker:	Human immunodeficiency virus (HIV) test will be performed at Screening	
Pregnancy test:	In women with childbearing potential a serum pregnancy test will be performed at Screening. A urine pregnancy test will be performed at Visit 1			

Approximately 15 to 20 mL (3 to 4 teaspoons) of blood will be collected each time at Screening, Evaluation period visits or upon discontinuation. In addition, before administration of the investigational drug, at Week 13, at Week 26, or upon discontinuation, approximately 3 mL (½ teaspoon) will be collected for the serum anti-SI-6603 antibody. All blood samples collected for the serum anti-SI-6603 antibody will be destroyed upon completion of the measurements of serum anti-SI-6603 antibody. If necessary, the blood samples collected for the serum anti-SI-6603 antibody will be used for assay development and will be destroyed upon completion of the assay development. All other blood samples collected will be destroyed at the end of the study or completion of all laboratory assessments. For serum anti-SI-6603 antibody, titer of SI-6603 specific antibody will be measured, and isotype of immunogloblin (IgG, IgM or IgE) will be identified on blood samples which contain SI-6603 specific antibody.

